#### **7.7.4.5 Other concomitant treatment**

Other medication than described above, which is considered necessary for the patient's safety and well-being, may be given at the discretion of the Investigator and recorded in the appropriate sections in the eCRF.

### **7.8 Post Study Access to Study Treatment**

After end of treatment with study drug, patients should be managed according to local standard of care.

## **8. STATISTICAL ANALYSES BY ASTRAZENECA**

### **8.1 Statistical considerations**

All personnel involved with the analysis of the study will remain blinded until database lock and protocol violators identified. Analyses will be performed by AstraZeneca or its representatives.

A comprehensive SAP will be prepared prior to database lock.

## **8.2 Sample size estimate**

Primary efficacy endpoint: A sample size of 450 subjects will have > 99% power to detect a 0.75 g/dL difference in mean Hb values between the two treatment groups, assuming that the common standard deviation is 1.2 g/dL, using an analysis of variance (ANOVA) test with a 0.05 two-sided significance level.

To contribute adjudicated CV safety events for the pooled CV analyses across the phase 3 program: approximately 2600 subjects are planned to be randomized in a 1:1 ratio to either roxadustat or placebo. The sample size in this study is driven by the overall requirement of adjudicated CV events for the phase 3 program in CKD-NDD (which consists of 3 studies in total targeting 465 subjects with MACE events). The two other placebo-controlled studies in the study program are FGCL-4592-060 and 1517-CL-0608.

Further information related to the sample size determination can be found in the study statistical analysis plan and the pooled statistical analysis plan.

## **8.3 Definitions of analysis sets**

### **8.3.1 Intention To Treat Analysis Set (ITT)**

All subjects who have been randomized to study treatment will be included irrespective of their protocol adherence and continued participation in the study. Subjects will be analysed according to their randomized study medication irrespective of intake of study medication.

### **8.3.2 Per Protocol Set (PPS)**

All randomized subjects without important protocol deviations and who have received at least 8 weeks of study treatment and have valid corresponding Hb measurements from the central laboratory will be included in the PPS. Subjects will be analysed according to their randomized study medication irrespective of intake of study medication. Subjects with an important protocol deviation will be included in the PPS up to the time point when the violation was met. For criteria for PPS exclusion, see Table 1 in the SAP. Further details of important protocol deviations are available in a Protocol Deviation Plan. Subjects will be censored at the earliest of date of an important protocol deviation, the EOS visit, or 28 days after last intake of study drug.

### **8.3.3 Safety analysis set**

All subjects who received at least one dose of randomized study drug will be included in the Safety Analysis Set. Throughout the safety results sections, erroneously treated subjects will be accounted for in the actual treatment group. If a subject has received both treatments, only the initial period will be utilized. Subjects will be censored 28 days after last intake of study drug. The Safety Analysis Set may also be referred to as On-treatment+28 (OT+28).

#### 8.3.4 Full Analysis Set (FAS)

The FAS consists of all subjects in the ITT analysis set who received at least one dose of study drug and have baseline and at least one post-dose Hb assessment. If actual study medication received differs from the randomized treatment arm, the randomized treatment arm will be used for analysis for the FAS. This analysis set is primarily used for EX-US submissions.

#### 8.3.5 Subjects who will not be included in any analysis sets

Subjects or sites identified prior to unblinding with major Good Clinical Practice violations and where the integrity of the data is strongly questioned through thorough independent investigations will be excluded from all analyses and all analysis sets. This includes but are not limited to subjects who have been identified to be part of a potential fraud investigation, subjects who have not signed an informed consent, subjects randomized in error (e.g. a subject considered to be a screen fail but by mistake randomized in the IWRS due to a technical error). Further, subjects being randomized more than once will only contribute to the analysis one time. These patients will be analyzed according to their first assigned randomization number and treatment code. All AE's reported for the subjects will be assigned to the subject's first randomization number. All subjects excluded from all analysis sets will be properly documented.

### 8.4 Outcome measures for analyses

#### 8.4.1 Primary efficacy endpoint

**US FDA:** The primary efficacy endpoint for the US is the mean change from baseline in Hb averaged over week 28 to week 52. A multiple imputation approach with analysis of covariance (ANCOVA) will be applied as a method to handle missing data. Details of the multiple imputation ANCOVA are provided in the SAP.

Hb results obtained from the central laboratory will be used for all Hb efficacy analyses. Baseline Hb is defined as the mean of the three last central laboratory Hb values from the screening and randomization visits.

Hb values under the influence of a rescue therapy will not be censored.

**EU health authorities:** The primary efficacy endpoint is whether patients achieved Hb response as described below.

- Hb response (Yes/No), where Yes is defined as:
  - Hb  $\geq$  11.0 g/dL and Hb increase from baseline by  $\geq$  1.0 g/dL, for subjects with baseline Hb  $>$  8.0 g/dL; or
  - Hb increase from baseline by  $\geq$  2.0 g/dL, for subjects with baseline Hb  $\leq$  8.0 g/dL

at two consecutive visits [dates] (with available data) separated at least 5 days during the first 24 weeks of treatment without having received rescue therapy (RBC transfusion, ESA, or IV iron) prior to Hb response. Subjects who have discontinued study medication or received rescue therapy before a Hb response could be achieved will be considered as a non-responder.

#### 8.4.2 Hb related secondary efficacy endpoints

The Hb related secondary efficacy variables are:

- The EU primary endpoint is the first secondary efficacy endpoint the analysis for FDA
- Mean change in Hb from baseline to the subjects mean level between week 28 to week 52 in subjects with baseline high-sensitivity C-reactive protein (hsCRP) greater than the Upper Limit Normal (ULN)
- Proportion of total time of Hb  $\geq$  10 g/dL from week 28 to week 52. The proportion of total time will be computed as follows: For each subject, the recorded Hb values will first be linearly interpolated between measurements. The time this interpolated curve is  $\geq$ 10 g/dL will be computed and subsequently divided by the time between the measurements at week 28 and week 52. Patients without any Hb measurements from week 28 will not be considered for this variable.
- Proportion of total time of Hb within the interval of 10-12 g/dL from week 28 to week 52. The proportion of total time will be computed as follows: For each subject, the recorded Hb values will first be linearly interpolated between measurements. The time this interpolated curve is within 10-12 g/dL will be computed and subsequently divided by the time between the measurements at week 28 and week 52. Patients without any Hb measurements from week 28 will not be considered for this variable.

#### 8.4.3 Lipid related secondary efficacy endpoints

To evaluate the roxadustat effect on lipids, the following variable will be evaluated

- Mean change in LDL cholesterol from baseline to week 24.

#### 8.4.4 Rescue therapy related secondary efficacy endpoints

The need for rescue therapy will be evaluated as:

- Time-to-first (and proportion of subjects receiving) instance of receiving intravenous (IV) iron, red blood cell (RBC) transfusions, or erythropoietin analogue as rescue therapy (rescue therapy guidelines are specified in the clinical study protocol (CSP), Section 7.7.4).
- Time-to-first (and proportion of subjects receiving) instance of receiving red blood cell (RBC) transfusions as rescue therapy.

and will be computed, as the number of days plus one between the day of first dose of study drug and the date of the first occurrence of rescue therapy, or if no event has occurred before censoring, the date of censoring.

#### 8.4.5 36-Item Short Form Health Survey

The SF-36 is a QoL instrument designed to assess generic health concepts relevant across age, disease, and treatment groups. It is aimed at both adults and adolescents aged eighteen years and older. The SF-36 consists of eight domains of health status: Physical functioning (10 items), Role-physical (4 items), Bodily pain (2 items), General health (5 items), Vitality (4 items), Social functioning (2 items), Role emotional (3 items) and Mental health (5 items). Two component scores, the Physical Component Summary and the Mental Component Summary can also be calculated. For both the SF-36 domain scores and summary scores, higher scores indicate better health status. The SF-36 has a recall period of the 'past four weeks'.

- Change from baseline in SF-36 Physical Functioning (PF) sub-score
- Change from baseline in SF-36 Vitality (VT) sub-score

The SF-36 scores will be computed according to its documentation

#### 8.4.6 CKD progression related secondary efficacy endpoints

To evaluate the effect of roxadustat on the CKD progression prior to initiation of dialysis/kidney transplant, the following variable will be analyzed:

- Annual rate of eGFR change in log scale, calculated as the slope of log (eGFR values), prior to initiation of dialysis/kidney transplant

### 8.5 Adjudicated CV Events Analyses for Safety Assessments

The CV events described in Section 5.2.1 will be adjudicated by the Independent Event Review Committee (IERC) according to the IERC charter. The same adjudication committee will be used for three phase 3 studies, FG-4592-060, 1517-CL-608 and D5740C00001, in the CKD-NDD program. Analyses of these adjudicated events are described in a separate pooled analysis plan.

## **8.6 Methods for statistical analyses**

A detailed Statistical Analysis Plan (SAP) will be finalized prior to database lock. Any significant changes to the analyses described in this protocol will be highlighted in the SAP and the Clinical Study Report (CSR). Moreover further details of the statistical analyses are provided in the SAP.

### **8.6.1 Stratification variables**

The randomization in this study will only be stratified by country. The stratification variables for the other two studies in the program will be used in the analyses for this study as covariates. The variables are:

1. Baseline eGFR ( $\leq 30$  mL/min/1.73 m^2 vs  $> 30$  mL/min/1.73 m^2)
2. Baseline Hb ( $\leq 8$  g/dL vs  $> 8$  g/dL)
3. cardiovascular/cerebrovascular/thromboembolic medical history (Yes vs. No)
4. geographical region (US vs Ex-US)

Baseline Hb and baseline eGFR will be included in the analyses as continuous covariates, not as dichotomous factors, unless specified otherwise. Throughout this document, the variable cardiovascular/cerebrovascular/thromboembolic medical history will be shortened as CV history.

CV history at baseline will be defined for subjects with history of any of the following diseases:

- Myocardial infarction
- Percutaneous coronary intervention
- Coronary artery bypass
- Cardiac failure congestive
- Ischaemic stroke
- Haemorrhagic stroke
- Cerebrovascular accident

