### **3.5 Methods for assigning treatment groups**

Randomization schedules will be prospectively prepared. Automated randomization and treatment assignments will be provided by an IWRS /IVRS. The randomization codes will be computer generated by AstraZeneca R&D using GRand (AZ Global Randomization system) and loaded into the IVRS/IWRS database. A block randomization schedule by country will be produced.

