## **7.2 Dose and treatment regimens**

### **7.2.1 Randomization**

Patients will be randomized to receive roxadustat or placebo in a 1:1 ratio in a double-blind manner. Randomization schedules will be prospectively prepared. Automated randomization and assignment to treatment arm will be provided by IWRS/IVRS. The randomization in this study will be stratified by country.

The number of tablet bottles that will be dispensed may vary depending on the dose. Dispensation will be managed by IWRS/IVRS. The administration will be detailed on a dosing card. Doses administered will be recorded in the eCRF.

The administration of the first dose of study drug would mark the beginning of the treatment period. Hemocue values will be used for all dose adjustments, including baseline values from Hemocue values at randomization. Missed doses should not be replaced.

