### **8.6.2 Analysis of the primary efficacy endpoint for US**

Mean change in Hb from baseline to the subjects mean level from week 28 to week 52 will be analysed with multiple imputation ANCOVA as described in the SAP. The model will contain

terms for the treatment, baseline Hb measurement, baseline eGFR, geographic region and CV history. Superiority of roxadustat compared to placebo will be declared, and this test as successful, if the lower bound of the 2-sided 95% confidence interval of the difference between roxadustat and placebo exceeds 0 g/dL. The ITT analysis set will be used.

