### 8.6.5 Analysis of the secondary efficacy endpoints

Secondary efficacy endpoints will be tested using a fixed sequence approach to adjust for multiple testing. If the p-value from a test is less than 0.05, the test will be declared as successful and the analysis will continue to the next comparison in the sequence. Formal statistical hypothesis testing will be stopped as soon as a test is accompanied by a p-value  $\geq$ 0.05. The FAS will be used on the first secondary endpoint, OT+28 will be used for the two secondary endpoints related to rescue therapy, and the ITT analysis set will be used for all the remaining secondary endpoints.

1. The EU primary endpoint is the first secondary efficacy endpoint for FDA (see above)
2. Mean change in Hb from baseline to the subjects mean level from week 28 to week 52 in subjects with baseline hsCRP greater than the Upper Limit Normal (ULN) will be analysed analogously as the primary efficacy endpoint. Superiority of roxadustat compared to placebo will be declared, and this test as successful, if the lower bound of

the 2-sided 95% confidence interval of the difference between roxadustat and placebo exceeds 0 g/dL.

3. Proportion of total time of interpolated Hb values  $\geq 10$  g/dL from week 28 until week 52 will be estimated for each subject and used as dependent variable. The difference between roxadustat and placebo will be compared using ANCOVA with treatment group, geographic region and CV history as fixed factors and baseline Hb and baseline eGFR as covariates. Superiority between the groups will be declared, and this test as successful, if the lower bound of the 2-sided confidence interval of the difference between roxadustat and placebo exceeds 0.
4. Proportion of total time of interpolated Hb values within the interval 10-12 g/dL from week 28 until week 52 will be estimated for each subject and used as dependent variable. The difference between roxadustat and placebo will be compared using ANCOVA with treatment group, geographic region and CV history as fixed factors and baseline Hb and baseline eGFR as covariates. Superiority between the groups will be declared, and this test as successful, if the lower bound of the 2-sided confidence interval of the difference between roxadustat and placebo exceeds 0.

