5. Mean change from baseline in LDL cholesterol to week 24 will be analysed using ANCOVA. Baseline Hb, baseline eGFR and baseline LDL will be used as covariates and treatment arm, CV history and geographic region as fixed effects. Superiority will be declared if the upper bound of the 2-sided 95% confidence interval of the difference between roxadustat and placebo exceeds 0.
6. Time-to-first (and proportion of subjects receiving) rescue therapy (composite) of any of IV iron, RBC transfusion or erythropoietin analogue as rescue therapy, will be analyzed using the Cox proportional hazard model with OT+28. Baseline Hb, baseline eGFR, geographic region, and CV history will be included as covariates. Superiority will be claimed, and this test successful, if the upper limit of the 2-sided 95% CI for the hazard ratio is less than or equal 1.0.
7. Time-to-first (and proportion of subjects receiving) RBC transfusion as rescue therapy, will be analyzed using the Cox proportional hazard model with OT+28. Baseline Hb, baseline eGFR, geographic region, and CV history will be included as covariates. Superiority will be claimed, and this test successful, if the upper limit of the 2-sided 95% CI for the hazard ratio is less than or equal 1.0.
8. Mean change in SF-36 Vitality (VT) sub-score from baseline to average VT sub-score of weeks 12-28 will be analyzed using MMRM with treatment, visit, treatment-by-visit interaction, and baseline covariates, including the baseline score, baseline Hb, baseline eGFR, and geographic region and CV history, as fixed effects and subject as a random effect. Superiority between roxadustat and placebo will be declared, and this test

successful, if the lower bound of the 2-sided confidence interval for the difference between roxadustat and placebo exceeds 0.

9. Annual rate of eGFR change in log scale prior to initiation of dialysis/kidney transplant will be estimated with MMRM using all post-baseline log (eGFR values) prior to initiation of dialysis/kidney transplant. Baseline eGFR in log scale, baseline Hb and geographic region, CV history, treatment group and post-baseline eGFR measurement time will be treated as fixed effects, and subject and time as random effects, i.e. random intercept and slope.

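### Country is the only randomization stratum, but the ANCOVA, SF-36 and Cox models carry geography only as US versus Ex-US; if country is prognostic, some precision is lost

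*Protocol*

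**What the plan says.** Three places in the protocol describe the randomization, and they agree. Section 3.5: "A block randomization schedule by country will be produced". Section 7.2.1: "The randomization in this study will be stratified by country". Section 8.6.1: "The randomization in this study will only be stratified by country".

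Section 8.6.1 then adopts as covariates the stratification variables of the other two studies in the programme. Geography appears in that list as "geographical region (US vs Ex-US"), so all non-US countries form one level.

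The later sections fix the terms model by model:

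- US primary ANCOVA (8.6.2): "terms for the treatment, baseline Hb measurement, baseline eGFR, geographic region and CV history". Secondary endpoint 2, the subset with raised hsCRP, is analysed in the same way.
- Time in Hb range, secondary endpoints 3 and 4 (8.6.5): "compared using ANCOVA with treatment group, geographic region and CV history as fixed factors and baseline Hb and baseline eGFR as covariates".
- LDL (endpoint 5) and SF-36 vitality and physical functioning (endpoints 8 and 10): region and CV history with baseline values, no country term.
- The two Cox rescue models (endpoints 6 and 7): "Baseline Hb, baseline eGFR, geographic region, and CV history will be included as covariates".

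The secondary endpoints are tested in a fixed sequence: "Formal statistical hypothesis testing will be stopped as soon as a test is accompanied by a p-value" of 0.05 or more.

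**The concern.** Blocking within country balances the arms on country and so removes between-country variance from the treatment contrast. A model without country leaves that variance in the residual. The reported standard error is then larger than the true one, and the test rejects too rarely under the null. The usual principle is to analyse by the factor used to randomize. Here that factor is missing from every model listed above.

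At stake is precision, not validity. The loss could matter in the secondary sequence, where an avoidable miss at one step closes all later steps. It arises only if country is prognostic beyond baseline Hb, baseline eGFR, CV history and US/Ex-US, and the protocol does not say whether it is.

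**Working it through.** **Inputs from the protocol.** About 2600 subjects randomized 1:1; two-sided alpha 0.05; for the primary endpoint, a difference of 0.75 g/dL, SD 1.2 g/dL and 450 subjects (section 8.2).

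**Assumed inputs.** The country share of residual variance (R²), the number and size of countries, the block size and the retained fractions are not in the protocol.

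**The plan's own figure.** SE = 1.2 × √(4/450) = 0.1131; 0.75/0.1131 = 6.63; power = Φ(6.63 − 1.96) = 0.999998. This agrees with the stated power above 99%.

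**1. Linear models on essentially the full randomized set** (US primary with multiple imputation; LDL and SF-36 as far as data are complete). With near-perfect balance within country, the true SD of the estimate is √(1−R²) times the model SE. Hence:

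- overstatement of the SE = 1/√(1−R²) − 1
- actual alpha = 2Φ(−1.96/√(1−R²))
- power = Φ(z + 1.96 − 1.96/√(1−R²)), with z = 0.842 for 80% or 1.282 for 90% when country is modelled

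| R² | SE overstated | Alpha | 80% becomes | 90% becomes |
|---|---|---|---|---|
| 0 | 0% | 0.050 | 80% | 90% |
| 2% | 1.0% | 0.048 | 79.4% | 89.6% |
| 5% | 2.6% | 0.044 | 78.5% | 89.1% |
| 10% | 5.4% | 0.039 | 76.9% | 88.0% |

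Simulation (N = 2600, 25 countries of 45 to 431 subjects, blocks of 4, 6000 runs) gave alpha 0.040 at R² = 10%. Another simulation, with the country variance defined after the US term, gave 0.046 and 0.038 at 5% and 10%, against 0.051 and 0.050 with country modelled. A third let the US/Ex-US term absorb part of the country variance; alpha was then 0.051, 0.050 and 0.044 at 2%, 5% and 10%. The effect is therefore smaller when much of the country variance is a US/non-US contrast.

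**2. Partly retained sets.** Endpoint 2 needs hsCRP from optional biomarker sampling (section 5.7), and endpoints 3 and 4 drop patients without Hb from week 28 (section 8.4.2). If a fraction p is retained at random, country is only partly balanced and alpha = 2Φ(−1.96/√(1−pR²)):

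- R² = 10%: 0.041, 0.044 and 0.047 at p = 80%, 50% and 30%.
- R² = 5%: 0.047 and 0.048 at p = 50% and 30%.

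The first simulation gave 0.047 and 0.043 at p = 50% and 30% with R² = 10% (Monte Carlo SE 0.003). That is compatible with the formula but too coarse to confirm the ordering.

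Country terms also cost something here. With 25 unpooled countries and no country effect, the SE rises by 0.0%, 0.1%, 0.5% and 1.1% at p = 100%, 80%, 50% and 30%. The net SE reduction for R² of 2%, 5% and 10% is 0.6%, 2.1% and 4.7% at p = 50%, and about 0%, 1.5% and 4.1% at p = 30%.

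**3. Cox rescue models.** Simulated with the same 25 countries and blocks and normal country effects on the log hazard, comparing a model with treatment and US/Ex-US against one stratified by country.

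| Country SD (log hazard) | Size, US/Ex-US | Log HR attenuated by | Power at HR 0.8, US/Ex-US vs stratified |
|---|---|---|---|
| 0.3 | 4.8–4.9% | about 1.0% | 80.5% vs 80.9% |
| 0.5 | 4.6% | 3.0–3.2% | 80.1% vs 81.9% |

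The stratified model had size 4.9–5.2%. Size used 20000 runs per scenario at about 15% and 25% with an event (Monte Carlo SE 0.15 points). Power used 12000 runs at about 25% with an event (paired Monte Carlo SE 0.14 and 0.17 points). At SD 0.5 a true HR of 0.50 is estimated near 0.51. Baseline Hb, eGFR and CV history were not simulated.

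**The case against.** The strongest reply is that this is a disclosed, pre-specified and valid choice. Section 8.6.1 says openly that the other studies' strata will be the covariates, and the version history gives harmonization across the programme as the reason. Every effect size above is assumed, the range begins at zero, and no secondary endpoint is shown to have moderate power. At small country effects the conservatism is hard to see: Cox size at SD 0.3 is within Monte Carlo error of 5%. Stratifying the Cox models also changes the hazard ratio being estimated and so its comparability across studies. The SAP, not seen here, may already contain a country-adjusted sensitivity analysis. The protocol version is dated 31 August 2018, close to the estimated study end in Q3 2018. Finally, the CMH test and the eGFR-slope model also omit country.

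Much of this stands, and it keeps the point minor. It does not justify leaving country out. Harmonization explains adding the other studies' covariates; it does not call for dropping this study's own stratum, and US/Ex-US models kept as supportive analyses preserve comparability. The SAP is to be finalized before database lock, so the change can still be made blind. The CMH test already has 2×2×2×2 = 16 cells; crossing these with 25 assumed countries would give 400 cells for 2600 subjects, about 6.5 each, so leaving it alone is reasonable. The eGFR-slope model was not worked through, and no change is asked there.

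**Conclusion.** The concern holds as a minor, conditional loss of precision. The fixed models omit the only randomization stratum. If country is prognostic beyond the listed covariates, the full-set linear tests are mildly conservative, the partly retained sets lose mainly precision, and the Cox tests are mildly conservative with a hazard ratio pulled slightly toward 1. For country shares up to 10%, the cost is at most about 3 points of power where it would otherwise be 80%. It is nil if country carries no extra information. These sizes rest on assumed country effects, country counts and block size, and on data missing at random with respect to country in the partly retained sets. Treating the US primary as a full-set analysis also assumes that imputed values behave like observed ones. No test is invalid and the US primary conclusion is safe.

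**What to change.** In the ANCOVA models (US primary and secondary endpoints 2 to 5) and the two SF-36 models, replace US versus Ex-US with country, pooling small countries within region by a rule fixed before unblinding. Use the same pooled groups in the raised-hsCRP subset, where unpooled country terms could cost more than they gain: at 30% retained, a share below about 2% brings no benefit without pooling. Stratify the two Cox rescue models by the same groups. Keep the US/Ex-US models as supportive analyses for programme harmonization.

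The cost is wording in sections 8.6.1, 8.6.2 and 8.6.5 and the pooling rule. Country is already recorded for randomization, so no new data are needed. The precision cost is nil in the full set and up to about 1.1% of the SE in a 30% subset with 25 unpooled countries; pooling reduces it.
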